Study Protocol

Home-based Resistance Training to Patients With Type 2 Diabetes

NCT04755660

Document Date: 2021.01.18

Study Protocol

Purpose: The purpose of the study is to explore the efficacy of a theory-based resistance exercise intervention and a resistance band exercise training on the level of physical activity, muscle strength body composition, exercise self-efficacy, and exercise adherence in adults with type 2 diabetes.

Methods: The study is a three-arm parallel randomized clinical trial. Participants were recruited from metabolism outpatient clinics. A total of 90 adults with type 2 diabetes were recruited and randomly assigned to the theory-based resistance exercise group, the resistance band exercise training group, or the control group. All groups underwent a 12-week intervention program. The theory-based resistance exercise group received a 12-week motivational interviewing and self-efficacy based resistance exercise training. The resistance band exercise group received a 12-week resistance band exercise training. All participants were introduced to exercise three times a week and at least thirty minutes a day on alterative day. The control group received a brief exercise instruction. Data were collected at the pretest, 6th week, and 12th week on handgrip strength, 6 meters walking speed (6 MWS), 30 seconds sit to stand (30' STS), self-reported physical activity, and exercise self-efficacy. The participants were asked to keep daily exercise dialog as well.

[name]
[contact]

新光醫療財團法人
新光吳火獅紀念醫院

SHIN KONG WU HO SU MEMORIAL HOSPITAL

E-mail : [contact]
[contact]

人體試驗委員會
同意人體研究證明書

計畫名稱：比較行為介入與居家阻力運動訓練對改善第二型糖尿病病人身體活動量與肌力之
成效：隨機分派臨床研究

計畫書編號/本會審查編號：20201202R

計畫書版本/日期：Version 3, 2021-03-03

計畫總主持人：[name]

計畫主持人所屬機構：新光醫療財團法人新光吳火獅紀念醫院台北護理健康大學

受試者同意書版本/日期：Version 2, 2020-12-28

通過會期：No.3/2021-3-11

核准效期：2021-01-18 至 2022-01-17

計畫追蹤頻率：每 12 個月一次。

期中報告繳交期限：2022-01-17(建議於前 6 週完成繳交以利期限前審畢)

結案報告繳交期限：2022-03-17(核准效期迄日後 2 個月內繳交)

其他：個案檢查資料登錄查核表 Version 2, 2020-12-28、運動日誌 Version 2, 2020-12-28、

個案招募篩檢表 Version 1, 2020-11-30、個案基本資料表 Version 1, 2020-11-30、

運動自我效能量表 Version 1, 2020-11-30、老人身體活動量表 Version 1, 2020-11-30、

招募海報 Version 1, 2020-11-30

Institutional Review Board
Approval of Human Study

Protocol Title : Comparing the Efficacy of a Behavioral Intervention and a Home-based Resistance Training of Physical Activity and Muscle Strength in Patients with Type 2 Diabetes:
A Randomized Clinical Trial

Protocol No./IRB No. : 20201202R

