**NCT04755660**

**Document Date: 2021.01.18**

## Statistical Analysis Plan

The results of this study were archived and analyzed with SPSS 22 package software, and the statistical significance level of Type I error was set at  $P<0.05$ , and the power was set at 80%. Every time the case data collection is completed, the data input and file building are completed on the same day. Before the data is analyzed, the distribution of each variable will be checked for outliers and missing values. Those who quit halfway are also encouraged to fill out the post-test questionnaire.

The basic attributes and disease characteristics of the research objects are presented in the form of frequency distribution, percentage, average value, and standard deviation. One-way ANOVA or Chi-Square test was used to examine the homogeneity of demographics, disease characteristics and pretest data of research variables among the groups. One-way ANOVA was used to examine the differences in blood glucose, body composition, muscle strength, physical activity, and self-efficacy scores between different groups between the sixth week and the 12th week. The t-test was used to examine the difference in exercise compliance between the behavioral intervention group and the home resistance training group. The generalized estimating equation (GEE) was used to analyze the differences in blood glucose, body composition, muscle strength, physical activity, and self-efficacy over time among different groups.

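### The SAP expects withdrawal but gives its GEE no working correlation or missing-data method, so outcome-related dropout that differs between arms could bias the week-12 comparison

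*SAP*

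**What the plan says.** The Methods paragraph of the Protocol describes three arms: "A total of 90 adults with type 2 diabetes were recruited and randomly assigned to the theory-based resistance exercise group", with a resistance-band group and a control group as the other two. On timing it says "Data were collected at the pretest, 6th week, and 12th week on handgrip strength", followed by walking speed, sit-to-stand, self-reported activity and exercise self-efficacy. On the comparator it says "The control group received a brief exercise instruction".

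The SAP's first paragraph deals with incomplete data in two places. Before analysis, "the distribution of each variable will be checked for outliers and missing values". On withdrawal, "Those who quit halfway are also encouraged to fill out the post-test questionnaire".

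Its second paragraph gives two between-group analyses of the outcomes. For weeks 6 and 12, "One-way ANOVA was used to examine the differences in blood glucose, body composition, muscle strength" and the remaining domains. For the longitudinal comparison among the groups, "The generalized estimating equation (GEE) was used to analyze the differences in blood glucose, body composition, muscle strength, physical activity", with self-efficacy completing the list.

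The public text states no expected dropout rate, analysis set, missing-data assumption, working correlation, weighting, imputation or sensitivity analysis.

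**The concern.** Unweighted GEE fitted to whatever visits are available is, in general, consistent only if dropout is unrelated to the outcomes, given the covariates in the model. With an independence working correlation and a group-by-visit mean model, the week-12 estimate for each arm is simply the mean of those who attended. The pretest and week-6 values of people who left then do nothing to correct it.

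In a home exercise trial, someone who sees little gain by week 6 may well stop. If that happens more in the training arms than in control, the training participants left at week 12 are a favourable selection, and a programme with no effect can look helpful. Unequal dropout is plausible, because control received only brief instruction, but nothing in the documents shows that it occurs.

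The safeguard for people who leave refers to a questionnaire. It could help with self-reported activity and self-efficacy. It says nothing about measuring grip strength, body composition or glucose in those who withdraw. The one-way ANOVA at weeks 6 and 12 is exposed in the same way if it uses attenders only.

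**Working it through.** The plan has no figure of its own to reproduce: 90 participants, alpha 0.05 and 80% power are given, but no effect size, SD or dropout allowance.

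**Inputs from the documents.** 90 participants, three arms, visits at pretest, week 6 and week 12.

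**Assumptions.** 30 per arm (the allocation ratio is not stated); outcome SD 1, with higher values better; no true effect; week-6 to week-12 correlation ρ of 0.5 or 0.7; complete pretest and week-6 data; 20% dropout after week 6. In training, the log-odds of dropout rise by 1.5 per SD of worse week-6 value. In control, dropout is random.

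**Step 1: selection among those who stay.** Let z be the week-6 value and p(z) = 1/(1 + exp(−(a − 1.5z))). Average dropout of 20% requires a = −1.916. The mean week-6 value of those who leave is ∫ z p(z) φ(z) dz / 0.20 = −0.906 SD. The overall mean is zero, so those who stay average 0.20 × 0.906 / 0.80 = 0.227 SD.

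**Step 2: bias at week 12 under independence GEE.** Bias = ρ × 0.227.
- ρ = 0.5: 0.11 SD
- ρ = 0.7: 0.16 SD

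A three-arm GEE simulation at ρ = 0.7 agreed: bias 0.161 SD, with the uncorrected robust test rejecting in 9.25% of 400 runs (95% interval about 6.8 to 12.5%).

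**Step 3: vary the assumptions that matter.**

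| Scenario | Calculation | Bias (SD) |
|---|---|---|
| Half the slope (0.75) in control | leavers average −0.551, stayers 0.20 × 0.551 / 0.80 = 0.138; ρ × (0.227 − 0.138) | 0.04 (ρ = 0.5) to 0.06 (ρ = 0.7) |
| Same mechanism in both arms | ρ × (0.227 − 0.227) | 0 |
| Asymmetry reversed | sign changes | −0.11 to −0.16 |
| Half of leavers measured in every arm | ρ × 0.10 × 0.906 / 0.90 | 0.05 to 0.07 |
| All leavers measured | nothing missing | 0 |

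Simulation of available week-12 means at ρ = 0.7 (20,000 runs) gave 0.058 SD and 5.4% rejection for half the slope, 0.000 and 5.1% for the same mechanism, and 0.072 and 5.7% with half of leavers measured.

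**Step 4: harsher settings.** With a slope of 2 and week-6 to week-12 correlations of 0.5 to 0.85, control dropout still random, independence GEE gave 0.13 to 0.22 SD and about 9 to 14% false positives at 20% dropout. Over 10 to 30% dropout it gave 0.07 to 0.32 SD and about 6 to 23%.

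**Step 5: other working correlations.** Exchangeable, when it matched the true correlation, gave 0.002 SD and 5.0% rejection. When dropout followed poor week-6 change and correlation decayed over time, exchangeable was biased by up to 0.17 SD. Unstructured left at most about 0.04 SD.

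**Step 6: likelihood-based model.** This shifts the stayers' week-12 mean by the regression on earlier values. At ρ = 0.7: 0.7 × 0.227 + 0.7 × (0 − 0.227) = 0. In the Step 4 simulations it was biased by no more than about 0.01 SD, with 4 to 6% false positives. If dropout instead followed the unseen week-12 value, 0.05 to 0.27 SD and 5 to 15% false positives remained.

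**Scale.** With 30 per arm, the pairwise difference detectable at 80% power (two-sided 5%) is (1.96 + 0.842) × √(2/30) = 0.72 SD. A bias of 0.11 to 0.16 SD is 15 to 22% of that.

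**The case against.** The strongest reply is that GEE as such is not at fault. A working correlation that fits the data removes most of the bias, and the SAP never says it will use independence. That is right, and a reader who infers that GEE makes this trial's result biased goes beyond the text. What stands is that the SAP names no structure, so the protection cannot be assumed, and a poorly fitting exchangeable structure can still fail.

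A second reply is that the direction is unknown. A reader might infer that the training arms must be favoured because only they have something demanding to abandon. The documents do not support that. The Protocol's Methods paragraph also says that every group underwent a 12-week programme and that all participants were introduced to exercise three times weekly. Dropout could be similar across arms, giving almost no bias under the null, or worse in control, reversing it.

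Third, a reader might think the bias persists however many leavers come back. It does not: it comes from missing measurements, and it vanishes if everyone is measured. The retention step therefore deserves credit for questionnaire outcomes.

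Fourth, the 9% error rate is imprecise and partly a small-sample effect, since robust GEE rejected in 5 to 7% of runs even under random dropout. The bias is the firmer result.

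Finally, the public documents are short, and the ethics approval cites a Version 3 protocol dated after them. The gap is established for the public text only.

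**Conclusion.** The point holds in a conditional form. The SAP foresees withdrawal, chooses a method whose validity depends on how dropout arises, and leaves open the settings that decide whether it is protected. The stated follow-up of people who leave does not extend to the physical and laboratory outcomes.

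The size depends on assumed dropout, correlation and asymmetry between arms: up to 0.11 to 0.16 SD in the main scenario, a third to two-fifths of that when control has half the dependence, and nil when the arms share one mechanism. Bias is a risk the plan leaves open. It is not a demonstrated result, and its direction is not known. The change is still worth making before analysis, because the alternative uses values already collected and performs at least as well in the scenarios tried.

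A reader might also infer that a likelihood model settles the matter. It does so only if dropout depends on observed values, which the data cannot confirm.

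**What to change.** For the continuous outcomes, specify a likelihood-based repeated-measures model with group, visit and group-by-visit terms; pretest, week 6 and week 12 as responses; unstructured covariance; and all randomised participants with any measurement. Take the week-6 and week-12 group differences from this model in place of both the GEE and the one-way ANOVA.

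If GEE is kept, specify a non-independence working correlation and first multiply impute missing week-6 and week-12 values by arm from the pretest and earlier visits.

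In either case, add a sensitivity analysis for dropout that depends on the unseen week-12 value, and report dropout by arm and visit.

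The cost is SAP wording and some analysis time. No new data are needed, and the planned package fits the model. The downside is reliance on approximate normality. The SAP's distribution check mentions only outliers and missing values, so a check of model residuals should be added.
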